## 1. Summary

Title:	Development and Validation of an Artificial Intelligence-based Biliary Stricture Navigation System in MRCP-based ERCP
Short Title:	EndoAngel Study
Trial number:	EA-19-003
Research system	EndoAngel
Expected effect:	ENDOANGEL's intended use is to instruct the direction of guide wire and the position of stent placement in real time.
Primary Endpoint:	Procedure time
Secondary Endpoints:	
 
1. Intersection over union of bile duct segmentation
 
2. Intersection over union of bile duct matching model
 
3. Success rate of stent placement
 
4. Rate of adverse events
 
5. Fluoroscopy time
 
6. Total amount of contrast medium
 

Trail design:	Prospective, single-center, randomized controlled trial
Participants:	Male and female subjects aged 18 years or older will require MRCP and ERCP, and voluntarily provide imaging data of MRCP and ERCP, and sign an informed consent form.
Sample size:	62 samples needed to be enrolled
Study Process:	Subjects who met all inclusion criteria and did not meet all exclusion criteria were included in the study before ERCP. All included subjects signed an informed consent form. Subjects will be randomized prior to the start of the examination to either an Endoangel-assisted experimental group or a control group without Endoangel assistance. The operating physician completed ERCP according to the presence or absence of AI prompt. The recorder shall record procedure time, intersection over union of bile duct segmentation, intersection over union of bile duct matching model, success rate of stent placement, rate of adverse events, fluoroscopy time and total amount of contrast medium etc. Follow-up will be performed for one week after the end of examination. The end time of follow-up is the end time of study. And the results are sent to an independent data analysis team for review.

[figure not shown]

[figure not shown]
Security	Safety incidents shall be evaluated and reported according to the quality management measures for clinical trials of medical devices
-----------------	--

### 1.1. Time and Event Tables

Events	Screening period (d -30~-1)	The day of ERCP(d 0)	Follow up (d 1-14)
Informed Consent	X		
Basic characteristics	X		
Medical history/surgical history	X		
Inclusion/Exclusion Criteria	X		
Random		X	
ERCP		X	
Concomitant treatment	X	X	
Concomitant medication	X	X	
Adverse Events		X	X
Research completed			X

### 1.2. Flow chat

## 2. Introduction

Biliary stricture can be divided into benign biliary stricture and malignant biliary stricture, and malignant hilar biliary obstruction is the one of the common cause. Since there is no specific early screening method for malignant hilar biliary obstruction at present and most patients have no obvious clinical symptoms in the early stage, most patients are already in the advanced stage when they are first diagnosed. Advanced malignant hilar biliary obstruction cannot undergo resection surgery, whose first choice for the treatment is palliative endoscopic biliary drainage. Biliary drainage can relieve jaundice, pruritus and other symptoms due to cholestasis. However, before the narrow segment was placed the stent, the contrast agent could not pass through the narrow segment and the bile duct above the narrow segment could not be seen. So it was difficult for doctors to determine the direction of the guide wire and the position of the stent. In addition, indiscriminate application of the contrast agent may cause outflow obstruction leading to infection. However, there is no relevant research to solve these problems.

MRCP is the preferred examination method of pancreatic and bile duct diseases. Therefore, MRCP should be routinely performed before patients are treated with ERCP. At present, MRCP is in supine position, and ERCP is in prone position. Different positions lead to differences in the morphology of MRCP and the bile duct on ERCP. So preoperative MRCP in supine position has limited role in advising physicians on the morphology of the bile duct. Therefore, MRCP in the prone position is more favorable for endoscopists to perform ERCP.

In recent years, deep learning algorithms have been continuously developed and increasingly mature. They have been gradually applied to the medical field. Computer vision is a science that studies how to make machines "see". Through deep learning, camera and computer can replace human eyes to carry out machine vision such as target recognition, tracking and measurement. Interdisciplinary cooperation in the field of medical imaging and computer vision is also one of the research hotspots in recent years. At present, it is mainly applied to the automatic identification and detection of lesions and quality control, and has achieved good results. It can assist doctors to find lesions, make disease diagnosis and standardize doctors' operations, so as to improve the quality of doctors' operations. With mature technical support, it has a good prospect and application value to develop endoscopic operating system for lesion detection and quality control based on artificial intelligence methods such as deep learning.

In this study, the investigators proposed an artificial Intelligence-based Biliary Stricture Navigation System in MRCP-based ERCP, which can instruct the direction of guide wire and the position of stent placement in real time.

## 3. Patient Selection

Male and female subjects aged 18 years or older will require MRCP and ERCP, and voluntarily provide imaging data of MRCP and ERCP, and sign an informed consent form.

Patients not meeting the inclusion criteria or meeting exclusion criteria will not be considered for participation in the study. Patients who met all criteria and signed informed consent may be excluded from the study due to:

- Endoscopists' professional advices/medical reasons (only under very limited conditions to avoid researcher bias).

- Withdraw informed consent.

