### **3.3. Definition of enrollment**

After participants signed informed consent, they were randomized before ERCP. The randomization time was the enrollment time, and was recorded in CRF.

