### **6.4 Suspension and withdrawal**

Patients who were screened and confirmed to be eligible for the study, signed the informed consent and completed the randomization were considered as enrolled. If serious program deviation, withdrawal, or death occurs, the subject study is considered to be suspended. If the subject discontinues the study after obtaining informed consent, the data before the discontinuation will still be included in the study-related analysis.

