#### **6.4.1 Pre-Procedure**

In any time during the study period, even before ERCP, participants could withdraw their informed consent whenever necessary. Researchers can withdraw participants before surgery according to safety considerations in the inclusion and exclusion criteria.

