## 6.5 Randomization and Blinding

### 6.5.1 Randomization Implementation

Randomization is conducted according to the study protocol, and the random contents are implemented in an electronic system block-randomized manner (n = 4; experimental group/control group = 1). Randomization prior to ERCP to decide whether to use EndoAngel. The researchers randomized the random results generated by the electronic system, and the generated random results were stored in the research center. The random time (accurate to minute), random person, subject number and acronym were recorded in the corresponding positions of the electronic system.

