### 6.5.2 Blinding Implementation and Protection

Subjects and evaluators are blinded according to the protocol.

Randomization results will be kept confidential to the subjects in general. Randomization results are not reflected in inpatient history and other subject access documents. During and after the examination, study personnel should take care not to talk to the subject about the results of the randomization to avoid unnecessary unblinding.

The assessors are blinded, and the data analysis team and pathologists could not obtain the randomization results from the medical history data.

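### Sections 3 and 6.4.1 set no cut-off at randomisation for discretionary exclusion, so patients can be removed after allocation and leave no primary outcome

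*Protocol*

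**What the plan says.** Section 3 introduces an override with the words "Patients who met all criteria and signed informed consent may be excluded from the study due to", and the first ground listed is "Endoscopists' professional advices/medical reasons (only under very limited conditions to avoid researcher bias". No time point is attached, and the conditions are not specified.

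Section 3.3 places allocation after consent and before the procedure: "After participants signed informed consent, they were randomized before ERCP". Section 1.1 puts consent in the screening period (day -30 to -1) and randomisation on day 0, the day of ERCP.

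Section 6.4 opens by defining enrolment: patients who were eligible, "signed the informed consent and completed the randomization were considered as enrolled". Within that section, 6.4.1 says: "Researchers can withdraw participants before surgery according to safety considerations in the inclusion and exclusion criteria". Section 6.4 also keeps data gathered before a discontinuation, and 6.4.3 rules out replacement.

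On blinding, Section 6.5.2 says: "Subjects and evaluators are blinded according to the protocol". The operator is not named there, and Section 1 says: "The operating physician completed ERCP according to the presence or absence of AI prompt". Section 6.5.1 describes "Randomization prior to ERCP to decide whether to use EndoAngel" and mentions no concealment of the result from the operator.

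Section 8.5 leaves an undefined category of culled cases out of the FAS and makes the PP set the main analysis.

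**The concern.** Randomisation protects the comparison only if whether a patient stays in the trial does not depend on the arm. Here two permissions to remove a patient have no end point at allocation. The primary endpoint is procedure time, which the operator produces, and Section 3 gives that same professional's advice as a ground for exclusion. If the operator knew the arm and expected a long case, a removal at that moment could differ between arms.

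The loss would be complete for the primary endpoint. Someone removed before ERCP has baseline data but no procedure time, so the rule in 6.4 that keeps earlier data has nothing to contribute. With 62 patients, a few such removals could matter.

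**Working it through.** **1. Does the permission reach past allocation?** The order of events is consent (screening), randomisation (day 0, before ERCP), ERCP (day 0).

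- Section 3 is conditional only on meeting the criteria and having consented. Both remain true after randomisation, so the wording does not stop there.
- Section 6.4.1 sits in a section that defines enrolled patients as randomised ones, and it runs up to surgery. It covers the interval between randomisation and ERCP, though only for safety considerations.

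**2. Could the removal depend on the arm?** The operator is not listed as blinded and works with or without the AI prompt, so the arm is known during ERCP at the latest. Knowledge before ERCP is an inference from the absence of any stated concealment.

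**3. Does another rule restore the patient?** Data before discontinuation contain no procedure time. The FAS may drop the patient as a culled case, and the PP set may drop the patient for a deviation. No section guarantees inclusion.

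**4. The plan's own sample size.** Inputs from Section 8.4: means 43.9 and 35 min (difference 8.9), SD 11.56, two-sided 5%, power 80%, dropout 10%.

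- Normal approximation: n per arm = 2 × (1.960 + 0.842)² × (11.56/8.9)² = 2 × 7.85 × 1.687 = 26.5, so 27.
- Two-sample t-test: 27.48 per arm; 27.48/0.9 = 30.5, so 31 per arm and 62 in total. The planned 62 is reproduced and is not in dispute.

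**5. Illustrative size.** Assumptions not in the protocol: procedure times are normal with SD 11.56 in both arms, there are 31 per arm, the k patients forecast to be slowest are removed from one arm only, and the forecast correlates ρ with actual time. Then

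shift in arm mean = ρ × SD × (sum of the k largest expected normal order statistics) / (31 − k).

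For n = 31 the three largest are 2.056, 1.632 and 1.383.

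- k = 2, ρ = 1: 11.56 × 3.688/29 = 1.47 min (1.47/8.9 = 16.5%)
- k = 3, ρ = 1: 11.56 × 5.071/28 = 2.09 min (23.5%)
- k = 2, ρ = 0.5: 0.73 min (8%)
- k = 3, ρ = 0.5: 1.05 min (12%)
- k = 2 or 3, ρ = 0.3: 0.44 or 0.63 min (5% or 7%)

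A simulation of 40,000 trials per setting agrees to within about 0.02 min. With no true effect and removals from the EndoAngel arm, it puts the chance of a significant result favouring EndoAngel (nominal 2.5%) at:

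| ρ | 2 removed | 3 removed |
|---|---|---|
| 0.3 | 3.5% | 4.1% |
| 0.5 | 4.4% | 5.6% |
| 1 | 8.0% | 11.8% |

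If both arms lost the same number of patients with the same accuracy of forecast, the shifts would cancel on average.

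**The case against.** A reader might infer that the protocol authorises the operator to drop hard cases after seeing the allocation. The documents do not support that.

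- The Section 3 clause stands under patient selection and does not mention randomised patients. Consent comes at least a day before randomisation, so there is a natural earlier window in which the clause could have been meant to apply.
- Section 6.4.1 is tied to safety, and its wording about withdrawal at any time concerns participants withdrawing their own consent.
- No section says when the operator learns the arm, or that MRCP forecasts procedure time.
- The figures of 1.5 and 2.1 min need perfect foresight and removal from one arm only, so they are a bound and not an expected bias.
- Some safeguards exist. Section 6.2.2 records the screening result and the main reason for not selecting a patient, 6.4.3 prevents swapping in an easier case, and 8.5 keeps shedding cases in the FAS.

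All of this stands as a limit on the strength of the claim, but it does not supply the cut-off. The remark in Section 3 about limited conditions shows that the risk was recognised, yet it names no condition, time point or independent decision-maker. The screening log does not govern removal after randomisation, and non-replacement makes the loss permanent. Nor is the override needed for clinical discretion at screening: exclusion criteria 4 and 5 in Section 3.2 already provide it.

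A further fair point is that 6.4.2 describes removal during the procedure, after allocation, more explicitly. Amending Sections 3 and 6.4.1 alone would therefore be incomplete.

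**Conclusion.** The point holds as a gap in the rules. The text permits exclusion or withdrawal after allocation by staff who are not blinded, and patients so removed before ERCP have no primary outcome. It does not instruct selective removal and gives no evidence that any is intended. That the operator knows the arm before ERCP remains an inference.

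On the stated assumptions, 2 or 3 one-sided removals shift the difference by about 0.7 to 1.0 min at a correlation of 0.5, with 1.5 to 2.1 min as the upper bound, against 8.9 min planned. The number removed, the correlation and the one-sidedness are all assumed. The effect is modest, but the direction is toward bias and the remedy is cheap, so the change should be made.

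**What to change.** 1. In Sections 3 and 6.4.1, state that discretionary or eligibility-based exclusion may happen only before randomisation, without knowledge of the arm, and with the reason entered in the screening record that 6.2.2 already requires.
2. State that after randomisation clinical decisions are unaffected, but the patient remains a trial subject. If ERCP is done, its procedure time and safety outcomes are recorded and analysed in the allocated arm.
3. Align 6.4.2 and the analysis sets in 8.5 with this, so that such patients are not lost as undefined culled cases or through reliance on the PP set for the main analysis. This concerns trial data only and leaves the clinical handling of an interrupted procedure as it is.

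The cost is a few sentences in four sections. The downside is that a few off-plan procedures stay in the data and slightly dilute the contrast between arms. Patients who never undergo ERCP will still lack a procedure time, but they will be counted and reported by arm.

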### 3.1. Inclusion criteria

All patients meeting the following criteria will be considered for participation in the study:

#### 1. Bile duct segmentation model

- 1) Male or female aged 18 or above;
- 2) Who needs ERCP, MRCP and its related tests are needed to further define the characteristics of digestive tract diseases;
- 3) The images of MRCP and ERCP are clear;
- 4) Able to read, understand and sign informed consent;
- 5) The investigator believes that the subject can understand the process of the clinical study and is willing and able to complete all the study procedures and follow-up visits and cooperate with the study procedures.

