#### 3. Clinical trials

In addition to the criteria mentioned in the bile duct segmentation model, the clinical trials should also meet the following criteria:

- 1) Able to complete MRCP in prone position;
- 2) Patients requiring biliary drainage by ERCP due to malignant hilar biliary obstruction.

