#### 2. Clinical trials

In addition to the criteria mentioned in the above, the clinical trial must not meet any of the following criteria:

- 1) Previous gastrectomy;
- 2) Stent replacement;
- 3) Pyloric or duodenal obstruction.

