## 8.5. Statistical analysis set

All patients who met the inclusion and exclusion criteria were considered eligible for recruitment.

The two analysis sets in this study are defined as follows:

- The full analysis set (FAS) population analysis set will contain all eligible cases and shedding cases, but does not include culling cases.
- The Compliance (PP) population analysis set will include all subjects in the FAS analysis set with no significant deviation from the program.

Intention-to-treat and conformity analysis sets should be used to analyze the primary efficacy endpoints. The main analysis will be based on the PP analysis set. FAS analysis was regarded as supportive analysis.

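### The randomised trial inherits an inclusion criterion on ERCP image clarity that cannot be judged until after randomisation, and section 8.5 leaves open removing patients on it

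*Protocol*

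**What the plan says.** Protocol section 3.1 has three lists of inclusion criteria: for the segmentation model, for the matching model and for the clinical trial. Item 3 of the first list reads "The images of MRCP and ERCP are clear". The clinical-trial list opens with "In addition to the criteria mentioned in the bile duct segmentation model, the clinical trials should also meet the following criteria" and makes no exception for that item.

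On timing, the table in section 1.1 puts the inclusion/exclusion check in the screening period, days -30 to -1, and both randomisation and ERCP on day 0. The Summary says "Subjects who met all inclusion criteria and did not meet all exclusion criteria were included in the study before ERCP". Section 3.3 says "After participants signed informed consent, they were randomized before ERCP", and section 6.5.1 says "Randomization prior to ERCP to decide whether to use EndoAngel". Section 6.4 adds: "Patients who were screened and confirmed to be eligible for the study, signed the informed consent and completed the randomization were considered as enrolled".

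On analysis, section 8.5 says "The full analysis set (FAS) population analysis set will contain all eligible cases and shedding cases, but does not include culling cases". The per-protocol set is a subset of the FAS and carries the main analysis; the FAS is supportive. The protocol does not define a culled case.

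**The concern.** An inclusion criterion should be decidable before allocation. Here one half of item 3 refers to images that, for a typical trial patient, do not yet exist when eligibility is judged. A site must either ignore that half or apply it after the randomised procedure.

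If it is applied afterwards, a randomised patient could be classed as ineligible on the basis of images from the very procedure whose duration is the primary endpoint. Clarity could be related to difficulty or to arm. The Introduction says that contrast may not pass the stricture and that the unseen duct above makes the guide wire hard to direct. Section 8.3 expects EndoAngel to change contrast use and fluoroscopy time. Visibility of the duct is not the same as image clarity, so this makes a link plausible and no more. Because the FAS is itself limited to eligible cases, the supportive analysis would not necessarily expose the problem.

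**Working it through.** **Step 1: can the criterion be applied when required?**

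| Question | Where | Answer |
|---|---|---|
| Does the trial inherit item 3? | 3.1, list 3 | Yes, without exception |
| When is eligibility checked? | 1.1 | Days -30 to -1 |
| When is the patient randomised? | 3.3, 6.5.1 | Before ERCP |
| When do the trial's ERCP images arise? | 1.1 | Day 0, during the procedure |
| Is an earlier ERCP required? | 3.1, 3.2 | No |

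The MRCP half can be assessed at screening; the ERCP half cannot. The exclusion "Stent replacement" in section 3.2 gives only minor support, since a patient might have had an earlier ERCP without a stent. The argument rests on no earlier ERCP being required.

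**Step 2: the plan's own figure.** Section 8.4 gives means of 43.9 and 35 minutes (difference 43.9 - 35 = 8.9), SD 11.56, two-sided 5%, power 80%, dropout 10% and a total of 62.

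- Normal approximation: n per arm = 2 × (1.960 + 0.842)² × 11.56² / 8.9² = 26.5, so 27. That is 54 in total, and 54/0.9 = 60.
- t test: 27.48, so 28 per arm and 56 in total. 56 × 1.1 = 61.6, so 62; 56/0.9 = 62.2, so 63.

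The 62 reproduces, and the inputs can be used below.

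**Step 3: what exclusion could do.** The protocol gives no rate of unclear ERCP images and no link to time, so both are assumed. The set-up was 200,000 simulated trials per scenario, no true effect, 31 per arm, times normal with mean 43.9 and SD 11.56, pooled t test at two-sided 5%. From one arm, k = 2, 3 or 4 patients are dropped (2/31 = 6% to 4/31 = 13%). The false-positive rate is one-sided, in the direction of the bias, nominal 2.5%.

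| Who is dropped (one arm) | Shift in that arm's mean, min (k = 2 / 3 / 4) | False positives |
|---|---|---|
| Random | 0.00 / 0.00 / 0.01 | 2.5 / 2.5 / 2.5% |
| Random within slowest third | -0.85 / -1.34 / -1.86 | 4.6 / 6.3 / 8.9% |
| The very slowest | -1.47 / -2.09 / -2.68 | 8.0 / 11.9 / 16.6% |
| Random within fastest third | +0.87 / +1.35 / +1.86 | 4.7 / 6.5 / 8.9%, against that arm |

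As a share of the planned difference, the slowest-third case is 0.85/8.9 = 10% to 1.86/8.9 = 21%; the worst case is 1.47/8.9 = 17% to 2.68/8.9 = 30%. For the slowest third, the two-sided error is about 6 to 9% against 5%.

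With equal exclusion in both arms the mean bias is within 0.02 minutes of zero. Two-sided error is 5.0–5.1% if patients are dropped at random or at random from the slowest third, and 7.2 / 8.1 / 8.8% if the very longest are dropped.

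**Step 4: power.** By the t test with the section 8.4 inputs, 62 analysed patients give 84.7%. Removing 10% gives 80.6% and 20% gives 75.7%. If 10% are removed on top of the planned 10% dropout, power is 76.2%.

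**The case against.** The strongest reply is that no passage orders such a removal and several point the other way.

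- Section 8.5 opens by tying eligibility to recruitment, and section 6.4 describes enrolled patients as already confirmed eligible. On that reading eligibility is fixed at randomisation. It is a fair reading, but the opening of 8.5 defines eligibility by the same criteria that include item 3, and neither section says that a patient cannot be reclassified for the analysis sets.
- Section 3 names only medical reasons and consent withdrawal as grounds for later exclusion. That list covers patients who met all criteria, not one judged to have failed a criterion.
- Section 6.5.2 blinds assessors and the data analysis team. This limits deliberate arm-specific exclusion, but does not help if clarity itself depends on arm or difficulty.
- The SAP, which is not at hand, may define culled cases. That stands: the missing definition is not itself the fault. The timing conflict is in the protocol's own text and remains.
- The larger figures assume losses in one arm and from the slow tail, and the one-sided presentation looks more severe than the two-sided 6 to 9%. This also stands; the figures are conditional illustrations.
- Keeping patients with unclear ERCP images would call for a rule on the intersection-over-union endpoints. Section 8.5 assigns the analysis sets to the primary efficacy endpoint, so that is a separate question and no reason to keep the criterion.

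The wider choices of a per-protocol main analysis and an FAS that is not all randomised patients are also separate from this point.

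**Conclusion.** The concern holds and should be fixed. The contradiction is certain: a stated inclusion criterion of the randomised trial cannot be assessed at the time the protocol requires. The consequence for the analysis is a possibility that the wording leaves open, not something the plan prescribes.

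Its size cannot be known from the protocol. Under the assumptions shown (no true effect, 2 to 4 of 31 lost from one arm), it runs from no bias, if clarity is unrelated to procedure time, to 0.9–1.9 minutes if losses come from the slowest third, and 1.5–2.7 minutes in the worst case. The direction could favour either arm. The planned sample size of 62 is not affected.

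**What to change.** In section 3.1, clinical-trial list, state that for the trial item 3 of the segmentation-model criteria is limited to the pre-procedure MRCP images. Keep the ERCP-image requirement for the two model-development datasets only. The image criterion can then be assessed before randomisation.

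In section 8.5, state that ERCP image quality is not a reason to remove a randomised patient from either analysis set.

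The cost is two lines of text. A few patients with poor ERCP images stay in the analysis of procedure time, and the sample size does not change.
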